6.0 TREATMENT PLAN

Treatment will be given according to the Schema described in section 6.1. A treatment may be stopped for up to 4 weeks to allow for recovery from toxicities. Patients unable to safely resume treatment at that point will be taken off study. 12 weeks constitutes one cycle of hormone therapy.

6.1 Treatment schedule:

- 6.1.1 Patients will begin radiation therapy only after they have demonstrated evidence of PSA normalization after initiation of androgen deprivation therapy (stable or declining PSA level of \leq 4 (or stable or declining PSA \leq pre-treatment level whichever is smaller) on two consecutive measurements. Patients who do not meet these criteria will be taken off protocol.
- 6.1.2 Patients will be divided into two strata:

Stratum 1:

a) Patients who are not on androgen deprivation therapy at the time of enrollment to the protocol will begin androgen deprivation and start radiation therapy after PSA normalization (see section 6.1.1)

b) Patients who are already treated with androgen deprivation therapy at the time of enrollment to the protocol (see 5.1.4) will continue androgen deprivation therapy and begin radiation after meeting criteria for PSA normalization (see section 6.1.1). Radiation therapy will be finished before 36 weeks (± 2 weeks) of hormone therapy is completed.

Stratum 2:

Patients who are enrolled on the protocol towards the end (or after completion) of 36 weeks (\pm 2 weeks) of androgen deprivation so radiation treatment cannot be finished before the completion of 36 weeks of androgen deprivation therapy can still initiate and/or complete radiation therapy as long as their serum testosterone level remains at the castrated levels (<50 ng/dL) and they meet the criteria for PSA normalization (section 6.1.1). Patients will not receive more than 36 weeks of androgen deprivation therapy.

- 6.2.4 All patients will be planned using helical tomotherapy given its ability to treat multiple sites with conformal RT in a single treatment session. However, at the discretion of the treating radiation oncologist, other technology, beam arrangements, photon energies and treatment plan is allowed if felt to be more appropriate for treatment of the specific lesion.
- 6.2.5 If previously untreated, the primary tumor (GTV = prostate gland) and potential areas of regional spread (GTV = seminal vesicles and pelvic nodes) are to be treated the PTV is the GTV + 5 mm margin and tomotherapy with daily 3-D image-guidance must be utilized. The total dose to the PTV will be 4500 cGy to the nodes, 4500 to 5400 to the seminal vesicles, and 7500 to 7800 to the prostate at 180-200 cGy/day.

6.3 Criteria for Removal From Treatment

- 6.3.1 Progression of disease at the time of androgen deprivation therapy (minimum of 12 weeks of treatment if progression is by PSA criteria only)
- 6.3.2 Patients do not meet the criteria for PSA normalization after 36 weeks of androgen deprivation (see section 6.1.1)
- 6.3.3 Unacceptable toxicity (as defined in section 7.0.)
- 6.3.4 Delay of treatment > 4 weeks from planned date of therapy due to toxicity.
- 6.3.5 Patient may always discontinue treatment whenever he wishes.
- 6.3.6 Patients will be taken off the protocol when they meet the criteria for PSA relapse following completion of 36 weeks of androgen deprivation therapy (see section 6.1.3)

7 TOXICITIES MONITORED, DOSAGE MODIFICATIONS

- 7.3 This study will use Common Terminology Criteria for Adverse Events v3, which can be found at the CTEP, website: http://ctep.cancer.gov/reporting/ctc.html
- 7.4 Management of Anticipated Toxicities: Missed days and doses will not be made up. Treatment should be stopped for any protocol treatment related Grade 3 toxicity or greater that cannot be controlled with good medical practice intervention. Treatment may be resumed upon resolution of that toxicity to Grade 2. A patient who experiences a Grade 3 or higher toxicity again will be removed from the study. There are no provisions for dose reductions of hormone therapy. The maximum delay in treatment will be 28 days.

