10.0 STATISTICAL CONSIDERATIONS

This is a phase II study to evaluate the efficacy and safety of radiation to metastatic sites plus 36 weeks months of androgen deprivation in patients with hormone-sensitive prostate cancer. The primary endpoint in this trial will be time to PSA relapse as defined in 9.2.8 and 9.4.4. Secondary endpoints include PSA response to treatment, safety, feasibility and tolerability.

Based on the prior data, the median time to PSA relapse (PSAR) following 36 weeks of androgen deprivation therapy, is approximately 40 weeks. This study would then look to detect an improvement beyond 40 weeks. For a one-sample, one-sided, 0.05-level test using the large-sample normal approximation for the distribution of the logarithm of the maximum likelihood estimator of the exponential parameter, with 28 patients and assuming accrual of 24 months and follow-up of 12 months, there will be 83% power for the test of the null hypothesis that the median PSAR is 9 months vs. the alternative that the median PSAR is 16 months as measured from the end of the twelve months of androgen deprivation therapy. If the parametric estimate of median PSAR is 13 months, this would suggest activity for the addition of radiation therapy. The initial analysis will include all patients, although analysis by strata will also be conducted in an exploratory fashion as will the role of previous adjuvant hormone treatment.

In addition to obtaining an early estimate of the effect of this therapy based on survival, feasibility and toxicity will also be carefully monitored in this novel approach.

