10.1 Interim analysis for toxicity

With 28 patients, we will be able to estimate the complication rate (any grade 3 or higher toxicity attributable to the radiation or combination of androgen deprivation/ radiation therapy) with a maximum standard error of 19%. If less than 2 cases have radiation induced complications, we can rule out a 17% complication rate or higher with 95% confidence. Since this therapy is not expected to cause severe toxicities, if at any time more than 25% of the patients experience a radiation induced complication, the study will be halted pending review.

The outcome status (in terms of toxicity, response, reason off study, progression, and survival) of all eligible patients who are registered will be reported. All patients who receive any treatment will be included in the summaries of toxicities. The CTCAE v. 3.0 toxicity criteria will be used. Toxicity information recorded will include the type, severity, time of onset, time of resolution, and the probable association with the study regimen. Time to progression and overall survival will be estimated using the product-limit method of Kaplan and Meier.

The sample-size, as justified above, is 28 patients. With an expected accrual of 14 patients per year, it will take approximately two years to complete the accrual.

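### Patients who leave treatment for toxicity are also taken off study, and nothing keeps them on the PSA schedule that the primary endpoint needs

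*Combined protocol and SAP*

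**What the plan says.** All references are to the combined protocol and SAP.

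- **Section 6.0** permits a hold: "A treatment may be stopped for up to 4 weeks to allow for recovery from toxicities". It continues: "Patients unable to safely resume treatment at that point will be taken off study".
- **Section 7.4** stops treatment for a Grade 3 or higher toxicity that is related to protocol treatment and not controllable by good medical practice. It then says "Treatment may be resumed upon resolution of that toxicity to Grade 2", and next "A patient who experiences a Grade 3 or higher toxicity again will be removed from the study".
- **Section 6.3** is headed "Criteria for Removal From Treatment". Item 6.3.3 is "Unacceptable toxicity (as defined in section 7.0"), and 6.3.4 is a toxicity delay of more than 4 weeks.
- **Section 8** schedules PSA every 4 weeks for 2 years and less often afterwards, until relapse. Toxicity grading is marked only for Day 1 of each 12-week cycle.
- **Section 9.0** restricts the analysis of time to PSA relapse to patients who complete radiation and one 12-week cycle of androgen deprivation on protocol. **Section 10.0** says: "The initial analysis will include all patients".
- **Section 9.4.4** starts the clock at the last bicalutamide dose or last radiation day, whichever is later, and gives no censoring rule. Sections 9.4.1 to 9.4.3 each give one.
- **Section 10.1** includes every treated patient in the toxicity summaries and asks for dates: "Toxicity information recorded will include the type, severity, time of onset, time of resolution".
- **After leaving the protocol**, section 6.1.3 promises a chart review. The schema and objective 5 list long-term follow-up, including PSA and long-term toxicity. None of these sets a schedule.

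**The concern.** Leaving treatment and leaving follow-up are different events, and the plan does not separate them. Sections 6.0 and 7.4 end study participation where 6.3 ends only treatment. In the schema, off study comes after follow-up to PSA relapse, so the phrase marks the end of the observation that produces the primary endpoint. A patient taken off study for toxicity before relapse would leave with that endpoint unobserved.

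Two things are at stake. The primary analysis rests on 28 patients with no stated margin for losses, and these losses would be caused by treatment rather than by chance. The plan also asks for resolution dates for toxicities while releasing the patients whose toxicities are most likely to be unresolved.

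**Working it through.** **1. Who is affected**

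| Patient | 6.0 / 7.4 | 6.3 | In the 9.0 analysis? | Scheduled PSA afterwards? |
|---|---|---|---|---|
| Recovers within a 4-week hold | Stays on study | Not listed | Yes, if he completes | Yes |
| Cannot resume, before finishing radiation and 12 weeks | Off study | Off treatment | No | None stated |
| Cannot resume, or Grade 3+ again, after finishing radiation and 12 weeks | Off study | Off treatment (delay over 4 weeks; recurrence only if it counts as unacceptable toxicity) | Yes | None stated |

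The third row is where the off-study wording itself costs data. By 9.4.4, the clock of a patient who stops early starts at his last bicalutamide dose or radiation day. Removal therefore falls close to time zero, and he contributes almost no follow-up. The second row is excluded by 9.0 even if he is followed perfectly; under the all-patients statement in 10.0 he would also be a loss.

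**2. The plan's power (section 10.0)**

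Inputs: n = 28; median 9 months (null) against 16 (alternative); one-sided 0.05; accrual A = 24 months; follow-up F = 12 months.

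Event probability with λ = ln 2 / median: p = 1 − [exp(−λF) − exp(−λ(A+F))] / (λA).

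- Null: λ = 0.0770, p = 0.819, expected events 28 × 0.819 = 22.94.
- Alternative: λ = 0.0433, p = 0.630, expected events 28 × 0.630 = 17.65.

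Power = Φ{[ln(16/9) − 1.645/√22.94] × √17.65} = Φ{(0.575 − 0.343) × 4.20} = Φ(0.974) = **83.5%**, which agrees with the stated 83%.

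**3. Power if k patients contribute nothing**

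The same formula with n = 28 − k. The documents give no removal rate, so k is an assumption.

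| k lost | Share of 28 | Expected events, null / alternative | Power |
|---|---|---|---|
| 0 | 0% | 22.94 / 17.65 | 83.5% |
| 1 | 3.6% | 22.12 / 17.02 | 82.4% |
| 2 | 7.1% | 21.30 / 16.39 | 81.2% |
| 3 | 10.7% | 20.48 / 15.76 | 80.0% |
| 5 | 17.9% | 18.84 / 14.50 | 77.3% |
| 7 | 25.0% | 17.20 / 13.24 | 74.2% |

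**4. Possible bias in the median**

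I simulated 100,000 trials per setting with exponential times and the plan's accrual and follow-up, and treated removed patients as contributing no data.

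- Removed patients have the same 16-month median as the rest: the typical estimate stays at 15.9 to 16.0 months for k from 0 to 7. With everyone at 9 months, the false-positive rate stays at about 3.7%.
- Removed patients have a 9-month median and the rest 16 (assumed): dropping them gives 15.9 to 16.0 months. Following everyone gives 15.3 (k = 2), 14.4 (k = 5) or 13.8 (k = 7). The overstatement is about 0.6 to 2.1 months.
- If removed patients had the longer median, the sign would reverse.

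**5. Complication rate**

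Section 10.1 counts a patient with any Grade 3 or higher toxicity attributable to radiation or the combination. A patient removed for a second such event is already in the numerator. The exact one-sided 95% upper bound for 1 of 28 is 15.9%, in line with the plan's ability to rule out 17%; it does not change with later follow-up of a patient already counted.

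**The case against.** The strongest reply is that this is loose wording. Section 6.3 treats the toxicity events as removal from treatment. The schema, objective 5 and section 6.1.3 foresee follow-up after patients leave. Section 10.1 requires outcome status, with reason off study, for every eligible registered patient, and section 12.3.4 provides a follow-up form. Follow-up therefore does not simply stop. That is right, but none of these provisions sets PSA dates or toxicity grading, and the chart review sits in the paragraph about patients who have already relapsed. The heading of 6.3 does not settle the matter either, because 6.3.6 under the same heading takes patients off the protocol.

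The reply also limits what may be concluded. A reader might infer each of the following, and the documents support none of them:

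- *Every patient whose treatment is held is lost.* Section 6.0 allows a hold of up to 4 weeks and 7.4 allows resumption, so patients who recover in time stay on study.
- *The complication rate is understated.* The index event is already counted and all treated patients are summarised. Scheduled grading is also thin for everyone once the cycles end.
- *Section 7.4 removes patients for unrelated or controlled events, or after treatment has ended.* The sentence does omit the qualifiers stated earlier in 7.4, but it follows directly on resumption of treatment and says the toxicity occurs again. Recurrence after resuming is the more natural reading. The scope is unclear and should be stated.
- *All the lost endpoint data come from 7.4.* The completer rule in 9.0 excludes early removals by itself.

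**Conclusion.** The point holds as a contradiction between 6.0 and 7.4 on one side and 6.3 on the other, with a real but conditional cost. Followed as written, the off-study rules lose time-to-PSA-relapse data from patients who qualify for the analysis, in a trial of 28 with no allowance for losses. Power falls from 83.5% to 80.0% with 3 lost and 74.2% with 7. These figures assume the plan's exponential model and that a removed patient contributes nothing; the number lost is my assumption.

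It is tempting to go further and say that the rules make the regimen look better. The documents give no outcome data for patients who leave for toxicity. The bias is nil if their prognosis matches the rest, about 0.6 to 2.1 months upward in the one adverse scenario above (2 to 7 removed), and downward if they do better.

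On safety, the per-patient Grade 3 or higher rate is largely protected. What can be lost is resolution dates, late toxicity, and a first radiation complication in a patient removed for another toxicity. That last patient would still count in the denominator of the 25% halting rule.

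**What to change.** 1. Reconcile 6.0, 6.3 and 7.4 so that leaving treatment and leaving the study are distinct. Supply the definition of unacceptable toxicity that 6.3.3 looks for in section 7, where there is none, and state which events the removal sentence in 7.4 covers. No change to when treatment stops is proposed here; the clinical rule is for the investigators to settle.
2. State that a patient who leaves treatment for toxicity stays on the section 8 PSA schedule until PSA relapse or restart of androgen deprivation, and has toxicity recorded until resolution, unless he withdraws consent.
3. Add a censoring rule to 9.4.4. Say also how relapse is defined for a patient who stops before 36 weeks, since 9.2.8 is worded for relapse after the 36 weeks are complete.
4. Reconcile the analysis sets in 9.0 and 10.0. Otherwise patients removed before completing radiation and 12 weeks are excluded even when followed, and item 2 does not recover them.

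The cost is protocol wording, plus a few additional toxicity assessments and PSA draws on a calendar that already exists. If all these patients are followed and analysed, the sample stays at 28 and the power at 83.5% under the plan's model.

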8.0 STUDY PARAMETERS AND CALENDAR

Assessment	Prior to Enrollment	Day 1 of each cycle [*]	Every 4 weeks until PSA relapse	At the time of PSA relapse
History and Physical Exam	X ¹	X ²		
Weight and WHO PS	X ¹	X ²		
Toxicity using CTC v3.0		X ²		
CBC, Diff, Plts, Na, K, Cl, CO ₂ , Creatinine, BUN, glucose, Calcium, phosphorus, albumin, LDH, SGPT (ALT), SGOT (AST), Alkaline Phos, Total Bilirubin	X ¹ X ¹	X ²		
EKG	X ³			
Chest X-Ray	X ³			
PSA	X ³		X^7	
Serum testosterone	X ³		X ⁸	
Tumor Measurements (measurable disease)	X ⁴	X^6		Х
Tumor Evaluation (evaluable disease)	X ⁵	X ⁶		Х
Treatment: LHRH agonist (goserelin or leuprolide)		q 4 weeks x 9 doses or q 12 weeks x 3 doses (total duration of androgen deprivation- see section 6.1) ⁹		
Treatment: bicalutamide		daily x 36 wee androgen depri	ks (total dur vation- see	ation of section 6.1) ⁹

Assessment	Prior to Enrollment	Day 1 of each cycle [*]	Every 4 weeks until PSA relapse	At the time of PSA relapse
Treatment: Radiation		daily x 2-7 weeks during or after completion of androgen deprivation therapy (see section 6.1)		

*Each cycle = 12 weeks

¹Within 7 days of d1 of cycle #1 (can be done on d#1 cycle #1)

²Except cycle 1 if done within 7 days of d1 of cycle #1

³Within 14 days of d1 of cycle #1

⁴Within 28 days of d1 of cycle #1

⁵Within 42 days of d1 of cycle #1

⁶At the time of completion of 36 weeks of androgen deprivation therapy or radiation therapy (whichever comes later) ⁷ Can be done on the day of clinic visit or up to 14 days before or after.

7 PSA; every 4 weeks for 2 years, and every 3mos after year 2, every 6 mos. thereafter or until relapse which ever occurs first.

⁸ Four weeks after the first LHRH injection, afterwards no repeat measurements will be done until the day of the last LHRH injection, and then monthly until the normalization of testosterone levels or resumption of androgen deprivation therapy (whichever comes first). Testosterone level will also be drawn to confirm castrated levels in patients who completed 36 weeks of androgen ablation and are considered for radiation therapy (see section 6.1.2.) To simplify schedule, testosterone level can be drawn on the same day that PSA test

 9 ± 2 weeks

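### Section 8 schedules no clinician toxicity grading at or after the end of radiation for stratum 2 and late-finishing stratum 1 patients, so the section 10.1 complication count may be somewhat low

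*Combined protocol and SAP*

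**What the plan says.** **Calendar (section 8.0).** "Toxicity using CTC v3.0" has a single mark, under day 1 of each cycle. History and physical has a mark there too, besides its pre-enrollment one. Footnote 2, which governs both day-1 marks, only waives cycle 1 when the assessment was already done "within 7 days of d1 of cycle #1". Footnote 6 moves an assessment to the end of hormone therapy or radiation, whichever is later, but it is attached to the two tumor rows only. The 4-weekly column holds PSA and testosterone. The relapse column holds tumor assessment.

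**Cycles and strata (section 6.0 and 6.1.2).** "12 weeks constitutes one cycle of hormone therapy". Stratum 2 consists of patients who enroll late, "so radiation treatment cannot be finished before the completion of 36 weeks of androgen deprivation therapy". For them, "Patients will not receive more than 36 weeks of androgen deprivation therapy". Stratum 1 radiation must finish before the 36 weeks (± 2) are over, but may finish close to that point.

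**Use of the data (section 10.1).** A complication is any Grade 3 or higher toxicity attributed to radiation or to the combination. Two statements rest on the count: "if at any time more than 25% of the patients experience a radiation induced complication, the study will be halted pending review", and "If less than 2 cases have radiation induced complications, we can rule out a 17% complication rate or higher with 95% confidence".

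**The concern.** The toxicity of interest is that of radiation, yet for all of stratum 2 and part of stratum 1 the last scheduled grading comes before radiation is complete. A complication that appears during the final fractions or in the following weeks is then counted only if someone notices or reports it. A site could follow the calendar exactly and still miss it.

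Objective 3 (toxicity) and both statements in section 10.1 depend on this count. Errors would run in one direction, towards a lower recorded rate and a later or absent halt. With 28 patients, one event can matter.

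**Working it through.** **1. When is the last scheduled grading?** Inputs: a 12-week cycle of hormone therapy, 36 weeks of hormones (section 6), and day-1 grading (section 8). The documents do not say where cycle 1 starts, so both anchors were tried.

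- Counted from hormone start: day 1 falls at weeks 0, 12 and 24, so the last is week 24.
- Counted from enrollment at hormone week w (0 to 35): day 1 falls at w, w + 12 and w + 24, kept while below 36. For w = 10 this gives 10, 22, 34; for w = 20 it gives 20, 32. Over all w, the last falls between weeks 24 and 35.

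Stratum 2 radiation is not finished before week 36, so no hormone-cycle day 1 follows it under either anchor. A stratum 1 patient is affected if radiation ends after the last day 1, which is week 24 under the first anchor and week 24 to 35 under the second.

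One case stays open. Stratum 2 admits patients who have already completed 36 weeks. If calendar cycles run from enrollment for them regardless of hormones, a patient enrolling at week 36 would have a cycle 2 day 1 at week 48. With 2 to 7 weeks of radiation (section 8) started at once, that is 5 to 10 weeks after the last fraction.

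**2. Reproduce the section 10.1 rule-out.** With n = 28 and a true rate of 17%:

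P(0 or 1 event) = 0.83^28 + 28 × 0.17 × 0.83^27 = 0.0054 + 0.0311 = 0.037.

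This is below 0.05, so the plan's statement is correct if every complication is counted. The exact one-sided 95% upper limit is 15.9% for 1 of 28 and 20.8% for 2 of 28. If one event is recorded and one is missed, the statement would be made when the true count does not support it.

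**3. Effect of incomplete capture on the rule-out.** The documents give neither the share of patients in stratum 2 nor the share of events that begin after radiation. The capture fractions below are assumptions. Recorded rate = 0.17 × capture.

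| Capture of true complications | Recorded rate | P(0 or 1 of 28) |
|---|---|---|
| 100% | 0.170 | 3.7% |
| 93.75% (one quarter in stratum 2, one quarter of their events missed) | 0.159 | 4.9% |
| 90% | 0.153 | 5.8% |
| 75% | 0.128 | 11.2% |

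The break-even capture is 0.1585 / 0.17 = 93%. Above it the 17% statement still holds at the 5% level.

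**4. Effect on the halt rule.** At 28 patients, 8 events (28.6%) exceed 25% and 7 events (25.0%) do not.

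- Mild case, true rate 35%: recorded rate 0.35 × (1 − 0.25 × 0.25) = 0.328. P(8 or more of 28) falls from 0.82 to 0.75. If the rule is checked after every patient from the eighth on (by simulation), it falls from 0.94 to 0.92.
- True rate 30%, single look at 28: 63.5% with full capture, 49.7% at 90%, 28.4% at 75%.
- True rate 10%, single look at 28: 0.5% with full capture, 0.3% in the mild case.

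**The case against.** The strongest reply is that Grade 3 or higher events are the hardest to overlook and that the protocol has several other ways to find them.

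- Section 16 defines adverse events as occurring during or after treatment and records those observed or reported. Serious events, which it describes as roughly Grades 3 to 5 when they meet a listed outcome such as hospitalization, are covered whether or not related.
- Section 7.4 requires action on Grade 3 or higher toxicity while treatment, including stratum 2 radiation, is under way.
- Section 12.3.3 asks for an adverse event form within four weeks of each course, and 12.3.4 for a follow-up form whenever new information arrives.
- Footnote 6 brings every patient to a tumor assessment at the right time, and complete response there requires absence of disease symptoms, so some clinical enquiry is implied.
- Section 6.1.3 adds chart review after patients leave protocol.

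This stands in large part. A reader might infer that no toxicity is collected after radiation; the documents do not support that. What these provisions lack is a date on which a clinician examines and grades the patient. A form deadline is not an assessment, and chart review after relapse comes too late for a halt decision about events before it.

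A reader might also infer that every stratum 2 patient certainly lacks a later grading. Section 6.0 and the opening of section 9.0 tie cycles to hormone therapy, but the calendar's own cycle footnote says only that a cycle is 12 weeks, and footnotes 1 to 5 date baseline tests from cycle 1 day 1. Patients enrolling after week 36 need some such date. The ambiguity is real.

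Finally, the finding depends on which rows carry footnote 6, and the available text of the calendar is imperfect, so the placement should be confirmed on the typeset page.

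**Conclusion.** The gap in the schedule holds on the plain reading: there is no dated clinician grading at or after the end of radiation for stratum 2, or for stratum 1 patients finishing after their last day 1. Patients enrolling after week 36 are a possible exception, depending on the cycle anchor.

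The section 10.1 rate and halt tally may therefore be somewhat too low. The size cannot be determined from the documents and is probably modest, because the unscheduled routes should catch many severe events. It would be tempting to conclude that the 17% rule-out or the halt rule is invalid. That does not follow: the rule-out reproduces, it survives capture down to about 93%, and in the mild case the halt probability changes by 0.07 or less. Larger losses would matter, but nothing in the documents shows that they would occur. The capture fractions, and the true rates used for the halt rule, are assumptions.

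This is a worthwhile, inexpensive correction to the calendar, not a flaw in the sample size or the safety thresholds.

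**What to change.** In section 8.0:

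1. Attach footnote 6 to the toxicity and history and physical rows, for both strata, so that every patient is examined and graded once hormones and radiation are both complete.
2. State in the calendar footnote whether cycles are counted from hormone start or from enrollment, and how this applies to patients who enroll after 36 weeks of hormones.

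The cost is up to one extra grading and examination per patient, 28 in total, at a time when tumor assessment is already due. Sample size, endpoints, treatment and the section 10.1 thresholds do not change.

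Repeated grading about every 12 weeks until PSA relapse would give better information on late effects and could be timed with the PSA draws ("every 4 weeks for 2 years, and every 3mos after year 2"). It is optional. At 3 contacts for a relapse at 9 months (39 weeks / 12) and 5 at 16 months (69 weeks / 12), it would add roughly 84 to 140 gradings over 28 patients, and a PSA draw need not involve a clinician.
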